**Table 4. Summary of Efficacy Analyses**

Endpoint	Estimand and Analysis Type	Population	Data Inclusion and Rules for Handling Intercurrent Events and Missing Data	Analysis Model
CHAQ - Discomfort Index responses change from DB baseline by DB visit	Estimand 7 Hypothetical Strategy  Secondary analysis	DBFAS	Only data collected On-investigational product are included.  Missing data are not imputed and handled using MMRM.	MMRM with terms treatment, visit, treatment*visit, DB baseline, DB baseline*visit
CHQ responses change from DB baseline by DB visit	Estimand 7 Hypothetical Strategy  Secondary analysis	DBFAS	Only data collected On-investigational product are included.  Missing data are On-investigational product not imputed and handled using MMRM.	MMRM with terms treatment, visit, treatment*visit, DB baseline, DB baseline*visit
sJIA ACR core set variables change from OL baseline by DB visit, including  • number of joints with active arthritis • number of joints with limited range of motion • physician global evaluation of disease activity • parent/legal guardian/subject evaluation of overall well-being (from the CHAQ) • ESR	Secondary estimand  Estimand 3 Treatment Policy Strategy  Secondary analysis	DBFAS	All data collected On- and Off-investigational product are included.  Missing data are not imputed and handled using MMRM.	MMRM with terms treatment, visit, treatment*visit, OL baseline, OL baseline*visit
	Estimand 7 Hypothetical Strategy  Supplementary analysis	DBFAS	Only data collected On-investigational product are included.  Missing data are not imputed and handled using MMRM.	MMRM with terms treatment, visit, treatment*visit, OL baseline, OL baseline*visit
CHAQ disability index change from OL baseline by DB visit	Estimand 7 Hypothetical Strategy  Secondary analysis	DBFAS	Only data collected On-investigational product are included.  Missing data are not imputed and handled using MMRM.	MMRM with terms treatment, visit, treatment*visit, OL baseline, OL baseline*visit

**Table 4. Summary of Efficacy Analyses**

Endpoint	Estimand and Analysis Type	Population	Data Inclusion and Rules for Handling Intercurrent Events and Missing Data	Analysis Model
sJIA ACR core set variables change from DB baseline by DB visit 

• number of joints with active arthritis

• number of joints with limited range of motion

• physician global evaluation of disease activity

• parent/legal guardian/subject evaluation of overall well-being (from the CHAQ)

• CHAQ disability index

• ESR

	Estimand 7 Hypothetical Strategy  Secondary analysis	DBFAS	Only data collected On-investigational product are included.  Missing data are not imputed and handled using MMRM.	MMRM with terms treatment, visit, treatment*visit, DB baseline, DB baseline*visit
CHAQ disability index change from DB baseline by DB visit	Secondary estimand  Estimand 3 Treatment Policy Strategy  Secondary analysis	DBFAS	All data collected On- and Off-investigational product are included.  Missing data are not imputed and handled using MMRM.	MMRM with terms treatment, visit, treatment*visit, DB baseline, DB baseline*visit
Steroid taper success in OL Part 2	Summary	OLPT2	Only use observed data	N/A
Steroid reduction to $\leq 0.2$ mg/kg/day or 10 mg/day in OL Part 2	Summary	OLPT2	Only use observed data	N/A
Adapted JIA ACR responses by OL Part 1 / 2 visit	Summary	OLPT1 / OLPT2	Only use observed data	N/A
JADAS-27 inactive disease CRP by OL Part 1 / 2 visit	Summary	OLPT1 / OLPT2	Only use observed data	N/A

**Table 4. Summary of Efficacy Analyses**

Endpoint	Estimand and Analysis Type	Population	Data Inclusion and Rules for Handling Intercurrent Events and Missing Data	Analysis Model
JADAS-27 inactive disease ESR by OL Part 1 / 2 visit	Summary	OLPT1 / OLPT2	Only use observed data	N/A
JADAS-27 minimal disease activity CRP by OL Part 1 / 2 visit	Summary	OLPT1 / OLPT2	Only use observed data	N/A
JADAS-27 minimal disease activity ESR by OL Part 1 / 2 visit	Summary	OLPT1 / OLPT2	Only use observed data	N/A
Absence of fever by OL Part 1 / 2 visit	Summary	OLPT1 / OLPT2	Only use observed data	N/A
JIA ACR inactive disease by OL Part 1 / 2 visit	Summary	OLPT1 / OLPT2	Only use observed data	N/A
JADAS-27 scores ESR (actual and change from OL baseline) by OL Part 1 / 2 visit	Summary	OLPT1 / OLPT2	Only use observed data	N/A
JADAS-27 scores CRP (actual and change from OL baseline) by OL Part 1 / 2 visit	Summary	OLPT1 / OLPT2	Only use observed data	N/A
CHAQ responses (actual and change from OL baseline) by OL Part 1 / 2 visit	Summary	OLPT1 / OLPT2	Only use observed data	N/A
CHQ responses (actual and change from OL baseline) at end of OL Part 1 / 2	Summary	OLPT1 / OLPT2	Only use observed data	N/A
JIA ACR core set variables (actual and changes from OL baseline) by OL Part 1 / 2 visit	Summary	OLPT1 / OLPT2	Only use observed data	N/A

**Table 4. Summary of Efficacy Analyses**

Endpoint	Estimand and Analysis Type	Population	Data Inclusion and Rules for Handling Intercurrent Events and Missing Data	Analysis Model
Fever attributed to sJIA on Day 3, 7 and 14 of OL Part 1	Summary	OLPT1	Only use observed data	N/A
Time to adapted JIA ACR30 response in OL Part 1	Summary	OLPT1	Only use observed data	N/A
CRP $\leq$ 10 mg/L by OL Part 1 / 2 visit	Summary	OLPT1 / OLPT2	Only use observed data	N/A

## Appendix 2. EFFICACY AND FUTILITY STOPPING BOUNDARIES

Efficacy: A 2-look Gamma family spending function with gamma parameter 4 is used to determine the efficacy boundaries.

Futility (non-binding): A 2-look Gamma family spending function with gamma parameter -4 is used to determine the futility boundaries.

Assumptions:

- True hazard ratio of tofacitinib vs placebo is 0.36
- Median time to flare for placebo is of 236 days

The efficacy and futility boundaries will depend on the number of flares. Boundaries when the number of flares at First Analysis is 28 are provided in [Table 2](#). Boundaries when the number of flares at First Analysis is 29-31 are shown below.

**Table 5. Stopping Boundaries at First Analysis Expressed as P-values and Number of Flares Needed at Final Analysis in Various Scenarios**

# Flares at First Analysis	28	29	30	31
Efficacy Boundary: 1-sided p-value $\leq$	0.0242	0.0245	0.0246	0.0247
Futility Boundary: 1-sided p-value $\geq$	0.1074	0.0815	0.0604	0.0506
# Flares Needed at Final Analysis	37	36	35	35
Overall Study Power (%)	80.4	80.5	80.9	81.8

### Efficacy and Futility Stopping Boundaries with 29 Flares at First Analysis Expressed as Hazard Ratio, Z Scores and P-values

Efficacy Stopping Boundary				
	Number of Flares	Hazard Ratio	Z-score	P-value (1-sided)
First Analysis	29	0.481	-1.969	0.0245
Final Analysis	36	0.425	-2.570	0.0051
Futility Stopping Boundary				
	Number of Flares	Hazard Ratio	Z-score	P-value (1-sided)
First Analysis	29	0.596	-1.395	0.0815
Final Analysis	36	0.425	-2.570	0.0051

### **Efficacy and Futility Stopping Boundaries with 29 Flares at First Analysis Expressed as Hazard Ratio, Z Scales and P-values**

Assuming a hazard ratio of 0.36 (tofacitinib vs placebo) and a median time to flare of 236 days for placebo  
Randomization ratio = 1:1, type I error rate (1-sided) = 2.5%, power = 80.5%

Efficacy boundary: gamma family spending function with  $\gamma = 4$

Futility boundary (non-binding): gamma family spending function with  $\gamma = -4$

### **Efficacy and Futility Stopping Boundaries with 30 Flares at First Analysis Expressed as Hazard Ratio, Z Scales and P-values**

Efficacy Stopping Boundary				
	Number of Flares	Hazard Ratio	Z-score	P-value (1-sided)
First Analysis	30	0.488	-1.966	0.0246
Final Analysis	35	0.425	-2.534	0.0056
Futility Stopping Boundary				
	Number of Flares	Hazard Ratio	Z-score	P-value (1-sided)
First Analysis	30	0.567	-1.552	0.0604
Final Analysis	35	0.425	-2.534	0.0056

Assuming a hazard ratio of 0.36 (tofacitinib vs placebo) and a median time to flare of 236 days for placebo

Randomization ratio = 1:1, type I error rate (1-sided) = 2.5%, power = 80.9%

Efficacy boundary: gamma family spending function with  $\gamma = 4$

Futility boundary (non-binding): gamma family spending function with  $\gamma = -4$

### **Efficacy and Futility Stopping Boundaries with 31 Flares at First Analysis Expressed as Hazard Ratio, Z Scales and P-values**

Efficacy Stopping Boundary				
	Number of Flares	Hazard Ratio	Z-score	P-value (1-sided)
First Analysis	31	0.494	-1.965	0.0247
Final Analysis	35	0.429	-2.503	0.0062
Futility Stopping Boundary				
	Number of Flares	Hazard Ratio	Z-score	P-value (1-sided)
First Analysis	31	0.555	-1.639	0.0506
Final Analysis	35	0.429	-2.503	0.0062

Assuming a hazard ratio of 0.36 (tofacitinib vs placebo) and a median time to flare of 236 days for placebo

Randomization ratio = 1:1, type I error rate (1-sided) = 2.5%, power = 81.8%

Efficacy boundary: gamma family spending function with  $\gamma = 4$

Futility boundary (non-binding): gamma family spending function with  $\gamma = -4$

## Appendix 3. DATA DERIVATION DETAILS

### Appendix 3.1. The JIA Core Set Variables

The sJIA ACR response determination is a derived measurement utilizing each component of the JIA core set variables, which include:

- Number of joints with active arthritis;
- Number of joints with limited range of motion;
- Physician global evaluation of disease activity;
- Parent/legal guardian/subject evaluation of overall well-being (from the CHAQ);
- Functional ability (Disability Index from the CHAQ);
- ESR. For “real-time” assessment of the Adapted JIA ACR30 response during a study visit the subject’s ESR will be used to determine the percent change in inflammation biomarker.

The ACR defines a joint with active arthritis as a joint with swelling or, in the absence of swelling, limitation of motion accompanied by pain on motion, or tenderness.

See details of the calculation of functional ability (disability index from CHAQ) in [Appendix 3.9](#).

### Appendix 3.2. The JIA Joint Counts

For swollen joints, painful/tender joints and joints with limitation of motion, respectively, before calculating the joint count, the following pre-processing step for each joint should be performed:

- If a joint receives an intra-articular injection (either at baseline or post-baseline visits), set the joint status to “Present” on or after the date of injection.
- If the site of injection is not recorded and/or cannot be identified, the joint assessment on the CRF (either “Present” or missing) will be used.

After this pre-processing, a joint assessment that is missing is considered “absent”, thus a good joint. To calculate the number of joints with active arthritis and the number of joints with limited range of motion, only “present” joints will be taken into account.

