### **5.3.2. Binary Endpoints**

For binary secondary endpoints in double-blind phase, intercurrent event will be handled as described in [Section 2.3.2.1](#) (Estimand 2) or [Section 2.3.4](#) (Estimand 6). After the intercurrent event is handled as appropriate, any remaining missing responses will be handled by setting the response value to nonresponsive for visits up to DB Week 52. This method of handling missing responses is known as missing response as non-response (MR=NR).

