### 5.3.2.2. JADAS-27 CRP, JADAS-27 ESR, and Occurrence of JADAS Minimum Disease Activity and Inactive Disease

For continuous measures (change from double-blind baseline in JADAS-27 scores), if any component is missing, then JADAS-27 CRP/ESR will be set to missing. These missing data will not be imputed otherwise and will be handled using the MMRM as described in [Section 5.2.3](#).

For binary assessments (occurrence of JADAS minimum disease activity and inactive disease), detailed definitions based on JADAS-27 CRP/ESR are in [Appendix 3.6](#). If JADAS-27 CRP/ESR value is missing, the corresponding binary assessments will be considered missing. Missing responses will not be imputed for descriptive summaries. For Estimand 2 analysis, missing responses will be handled as described in Section 5.3.2.

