### 5.3.2.3. Presence of JIA ACR Inactive Disease and Clinical Remission

Calculations of JIA ACR inactive disease using ESR are as in [Appendix 3.7](#). If any of the components is missing, the components that are not missing will be used to determine the Clinical Inactive Disease Status as follows:

- Inactive disease: all components must be present (non-missing) and meet all conditions.
- Active disease: at least one component is present (non-missing) and does not meet the condition.
- Not determined: any other scenarios.

Clinical remission will be derived from inactive disease except when LOCF is applied in Estimand 2 as described in [Section 2.3.2.1](#). Clinical remission corresponds to at least 24 weeks of inactive disease continuously while on investigational product (for evaluation of this endpoint in the double-blind phase, the counting of 24 weeks starts from the double-blind phase Day 1).

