#### **Appendix 3.4. The Adapted JIA ACR30-50-70-90-100 Response**

The disease activity of sJIA will be measured using an adaptation of the JIA American College of Rheumatology (ACR) 30 response ([Giannini 1997](#)). The Adapted JIA ACR30 Response criteria include the components of the pediatric ACR core set ([Appendix 3.1](#)) along with the absence of fever, defined as temperature  $\leq 38^{\circ}\text{C}/100.4^{\circ}\text{F}$  in the preceding 7 days. The Adapted JIA ACR30, 50, 70, 90, 100 response is defined as the absence of fever due to sJIA (oral temperature  $\leq 38^{\circ}\text{C}/100.4^{\circ}\text{F}$ ) in the preceding 7 days along with at least 3 out of 6 JIA core set variables improved  $\geq 30\%$ , 50%, 70%, 90%, 100%, respectively, with no more

than 1 out of 6 JIA core set variables worsened by >30%. Only ESR will be used to calculate Adapted JIA ACR responses.

The Adapted JIA ACR30, 50, 70, 90, 100 response will be determined at every visit from Day 7 onward based on the investigator's and parent/legal guardian's assessment of components of the JIA core set variables.

If the value in any of the components at a timepoint is missing, the component variables that are not missing will be used to determine the response status. As a general principle, if there are sufficient non-missing components to determine whether the JIA ACR endpoint is a response or non-response, then JIA ACR endpoint is not missing, else if the available non-missing components are not sufficient to determine the response status of JIA ACR endpoint then it is considered missing.

In order to avoid numerical difficulty, if the baseline value of any component is equal to 0, the following algorithm will be used in evaluating the percent change from baseline:

1. If change from baseline is also equal to 0, then percent change from baseline is set to be 0%;
2. If change from baseline is > 0, then percent change from baseline is set to be 999999%.

These percentages will be used to derive the JIA ACR endpoints. Change from baseline cannot be < 0 since none of the components should have negative value.

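### SAP Appendix 3.2 scores an unassessed joint as unaffected with no exception for an exam not done, so a skipped joint exam gives zero counts and can bypass the SAP's own missing-data rules for secondary endpoints

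*SAP*

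**What the plan says.** SAP Appendix 3.2 works joint by joint. After a step for injected joints it states: "After this pre-processing, a joint assessment that is missing is considered" absent. It then says that "only “present” joints will be taken into account" when the number of joints with active arthritis and the number with limited motion are calculated. No minimum number of assessed joints is set, and nothing is said about an exam that was not done.

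Other parts of the SAP treat missing data differently:

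- **Core set variables (Section 5.3.3):** missing values are left to the MMRM and not otherwise imputed. Both joint counts are core set variables.
- **JIA ACR inactive disease (Section 5.3.2.3, repeated in Appendix 3.7):** "Inactive disease: all components must be present (non-missing) and meet all conditions".
- **JADAS-27 (Section 5.3.2.2 and Appendix 3.5):** "if any component is missing, then JADAS-27 CRP/ESR will be set to missing".
- **Adapted JIA ACR response (Sections 5.3.2 and 5.3.2.1):** the response is missing only if the available components cannot settle it. In the double-blind phase, a response that is still missing up to Week 52 is then set to non-response (MR=NR).

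Double-blind flare follows another route. It is taken from the CCC's real-time assessment, and a missing component is filled from the previous visit when flare cannot otherwise be determined (SAP Sections 5.2 and 5.3.1, Appendix 3.3).

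**The concern.** The convention acts before every component-level rule listed above. If a blank always becomes a good joint, the joint components can never be missing, so they can never trigger those rules. A skipped exam is given the best possible value on two of the six core components.

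The endpoints exposed are those the sponsor derives itself:

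- **Joint-count changes (MMRM):** these have no second component that could keep the value missing.
- **Adapted JIA ACR responses:** imputed zeros can settle a response before MR=NR is reached.
- **JIA ACR inactive disease:** the condition of no active joints is met by default.
- **JADAS-27:** the joint part contributes 0 of a possible 27.

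In the open-label summaries MR=NR does not apply. Percentages are taken over subjects with non-missing values (SAP Section 6.2.2). A subject who should leave the denominator at a visit may instead be counted as a responder.

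**Working it through.** The documents give no figure for missing joint exams, so there is no plan figure to reproduce. What can be checked is what the rule does when the exam is missing and the other components are present.

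**Inputs**

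- Two of the six core components are joint counts: active arthritis and "Number of joints with limited range of motion" (SAP Appendix 3.1).
- ACR30 response needs no fever, "at least 3 out of 6 JIA core set variables improved" by at least 30%, and at most one worsened by more than 30% (SAP Appendix 3.4).
- A component that is 0 at baseline and unchanged has 0% change (SAP Appendix 3.4).
- The reference is the open-label baseline (SAP Section 3.4). Entry requires at least 2 active joints with fever, or at least 5 (protocol Section 4.1). With baseline B ≥ 2, a count of 0 gives (0 − B)/B = −100%.
- No entry minimum applies to limited-motion joints, so that baseline may be 0.

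**Enumeration.** Assume no fever and a missing joint exam. Each of the other four components (physician global, parent global, CHAQ disability index, ESR) is improved, stable or worsened: 3⁴ = 81 patterns.

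*A. Joint counts kept missing.*

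- With none of the four improved, at most 2 of 6 can improve, so the result is a non-response.
- With two or more worsened, it is also a non-response.
- Otherwise the result is open. It is a response if both missing counts improved, and a non-response if both worsened.
- Open patterns: none worsened, 2⁴ − 1 = 15; exactly one worsened, 4 × (2³ − 1) = 28; total 43.
- Definite non-responders: 81 − 43 = 38. Definite responders: 0. MR=NR sends the 43 open patterns to non-response.

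*B. Appendix 3.2 as written, both baselines above 0.* Both counts are improved by 100%. A response then needs at least one of the other four improved and at most one worsened. That is the same 43 patterns, and all become responders.

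*C. Appendix 3.2 as written, limited-motion baseline 0.* One count is improved and one is unchanged, so at least two of the other four must improve. None worsened: 6 + 4 + 1 = 11. One worsened: 4 × (3 + 1) = 16. Total 27 responders; the other 16 open patterns become non-responders.

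| Handling of the missing exam | ACR30 responders, of 81 |
|---|---|
| Counts missing, then MR=NR | 0 |
| Appendix 3.2, both baselines > 0 | 43 |
| Appendix 3.2, limited-motion baseline 0 | 27 |

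The patterns are not equally likely, so 43/81 is not a rate. As an illustration only, assume that each of the four improves independently with probability p and that none worsens. Case B gives 1 − (1 − p)⁴ = 0.34, 0.76 and 0.94 for p = 0.1, 0.3 and 0.5. Case C gives 1 − (1 − p)⁴ − 4p(1 − p)³ = 0.05, 0.35 and 0.69. Case A gives 0 throughout.

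**Higher levels.** A fall to zero counts as improvement at every level up to ACR 100, but the remaining improved component must itself reach that level.

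**Wholly missed visit.** Two imputed improvements with nothing else known leave the response open. It stays missing, and MR=NR gives non-response.

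**The case against.** The strongest objection concerns what a blank means. For an injected joint whose site cannot be identified, Appendix 3.2 says "the joint assessment on the CRF (either “Present” or missing) will be used". No recorded absent value is named there. A blank may therefore be how the CRF records an unaffected joint, and the rule would then decode the form. The CRF is not in the documents, so this is open. It is a good reason not to carry forward or prorate single joints: if blank means unaffected, carry-forward would keep resolved joints active and proration would distort every count. It does not answer the case of an exam not done, which becomes harder to tell apart from a clear exam.

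The convention is also written for single joints, while the conflicting rules concern components and responses. The zero count for a skipped exam follows from the text as written; the SAP does not state it.

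A reader might infer more than the documents support:

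- **That MR=NR is overridden.** It is bypassed only when the other components are favourable enough; 38 of the 81 patterns do not change.
- **That telephone visits create responders.** Protocol Appendix 10 says that Adapted JIA ACR response cannot be assessed by telephone. The minimum call content includes no core-set measure, so in the double-blind phase the response stays open and becomes a non-response.
- **That inactive disease and JADAS-27 are widely affected.** Physician global is rated after the joint assessment (protocol Section 8.1.3). If it is missing too, that alone blocks inactive disease and makes JADAS-27 missing.
- **That the bias always favours response, or favours tofacitinib.** Joints left blank at open-label baseline lower the baseline count and work against response. The documents do not show a direction between arms.

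The CCC receives the joint form at each visit and may query the site (protocol Section 8.1.12), which should make unnoticed skipped exams less common.

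**Conclusion.** The point holds for sponsor-derived secondary endpoints at visits where the joint exam was skipped but other components were collected. There the SAP gives two incompatible instructions. The one applied first puts the best possible value on both joint counts. For ACR30 with no fever, that turns 43 of 81 component patterns (27 if baseline limited motion was 0) from non-response into response.

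This rests on reading Appendix 3.2 as written, with no unstated exam-level check in the programming, and on correctly recorded baseline counts. How often it would happen cannot be estimated from the documents. A reader might extend the point to the primary result, but the documents do not support that: time to flare and its log-rank test use CCC assessments and do not pass through Appendix 3.2.

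**What to change.** State in Appendix 3.2 that missing-is-absent applies only when the joint exam was performed. When it was not done, set both joint counts to missing. MR=NR, the MMRM and the component rules for JADAS-27 and inactive disease then apply as already written. Reconcile Appendix 3.2 with Sections 5.3.2 to 5.3.3 and Appendices 3.5 and 3.7, and name the CRF item that shows the exam was done. This is right under either meaning of a blank.

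Do not add per-joint carry-forward or proration unless the CRF records 'not assessed' separately from 'absent'. Partly completed exams cannot be settled without knowing that.

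The cost is a short SAP edit and a programming change, best made before unblinding. A few responses may become non-responses or missing.
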